In Cohort B the safety evaluation will be performed by an IDMC after the first 10 patients completed at least 5 weeks of combination treatment. The evaluation will be done by the IDMC as already described. Importantly, all patients in Cohort B, who participate in the safety run-in phase, will be hospitalized on the day of the first two dose escalations of venetoclax (C1D8 and C1D15).

The criteria for the evaluation of safety of the combination therapy will be defined by the IDMC and laid down in the IDMC Charter of the trial.

If safety evaluation results in a recommended dose reduction of idelalisib or venetoclax, the sponsor will reconsider dosing and amend the protocol accordingly.

During the study, MOR00208 will be administered as infusions 12.0 mg/kg in 28-day cycles. From Cycle 1 to 3, each cycle will consist of weekly infusions (on Day 1, Day 8, Day 15 and Day 22). In Cycle 1, an additional loading dose will be administered on Day 4. From Cycle 4 to 6, MOR00208 will be administered on a biweekly basis with infusions on Day 1 and Day 15

of each cycle. Thereafter, MOR00208 will be administered on Day 1 of each cycle starting with Cycle 7 Day 1.

Idealisib will be self-administered twice daily starting on Day 1 of each cycle. Venetoclax will be self-administered (except during hospitalization) starting from Cycle 1 Day 8 and on Day 1 of each cycle onwards. Treatment with idelalisib or venetoclax may be modified in a de-escalating fashion or discontinued based upon clinical and laboratory findings. In case idealisib or venetoclax treatment was stopped due to side effects suspected to be related to idealisib or venetoclax, the patient may continue MOR00208 treatment.

Progressive disease will require discontinuation of study medication.

[figure not shown]
Patients who benefit from treatment are allowed to continue MOR00208 treatment beyond Cycle 24 at Investigator's discretion. The total duration of the main study will be limited to a maximum of 5 years from first patient first visit or up to the timepoint of approximately 30 days after last patient received his last treatment, whichever comes first.

Patients completing the main study will be invited to participate in an optional biological marker sub-study as described in detail in Section 15.13 Appendix M.

MorphoSys AG Proprietary Information

nation

Figure 1: Study Design

*1 Additional loading dose of MOR00208 on Cycle 1 Day 4

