If there is uncertainty regarding whether there is true progression, the subject should continue study treatment and remain under close observation. In particular, worsening of constitutional symptoms in the absence of objective evidence of worsening CLL will not be considered definitive disease progression; in such subjects, both CLL-related and non-CLL-related causes for the constitutional symptoms should be considered. Worsening of disease during temporary interruption of study treatment (e.g., for intercurrent illness) is not necessarily indicative of resistance to study treatment. In these instances, CT or MRI or other relevant evaluations should be considered in order to document whether definitive disease progression has occurred. If subsequent evaluations suggest that the subject has experienced persistent definitive CLL progression, then the date of progression should be the timepoint at which progression was first objectively documented.

Lymphocytosis During Therapy

Upon initiation of idelalisib treatment, transient increase of absolute lymphocyte count is expected in most patients because idelalisib can mobilize CLL cells from tissues into the peripheral blood. This characteristic pharmacological action can be prominent early in therapy but can persist over time and should not be confused with disease progression in subjects who have persistent control of other CLL-related signs and symptoms. **In the absence of other objective evidence of disease progression, lymphocytosis alone will not preclude subjects from meeting the criteria for PR if other criteria for PR are met and will not be considered evidence of disease progression if occurring in isolation.** Thus, subjects with worsening lymphadenopathy, organomegaly, bone marrow involvement, progressive cytopenias, appearance of new disease, or transformation to a more aggressive lymphoid malignancy histology (e.g., Richter's syndrome) will be considered to have progressed according to IWCLL criteria for progressive disease. Subjects with lymphocytosis without any of these other events will not be considered to have progressed and should be continued on study drug until the occurrence of definitive disease progression (Note: PRL is applicable in Cohort A only).

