15.10 Appendix J: Response Definition for CLL by the IWCLL Guidelines 2008

Parameter	CR*	PR*	PD*
Group A			
Lymphadenopathy†	None > 1.5 cm	Decrease ≥ 50%	Increase ≥ 50%
Hepatomegaly	None	Decrease ≥ 50%	Increase ≥ 50%
Splenomegaly	None	Decrease ≥ 50%	Increase ≥ 50%
Blood lymphocytes	< 4000/μL	Decrease ≥ 50% from baseline	Increase ≥ 50% over baseline
Marrow‡	Normocellular, < 30% lymphocytes, no B-lymphoid nodules Hypocellular marrow defines CRi	50% reduction in marrow infiltrate, or B-lymphoid nodules	--
Group B			
Platelet count	> 100,000/μL	> 100,000/μL or increase ≥ 50% over baseline	Decrease of ≥ 50% from baseline secondary to CLL
Hemoglobin	> 11 g/dL	> 11 g/dL or increase ≥ 50% over baseline	Decrease of > 2 g/dL from baseline secondary to CLL
Neutrophils‡	> 1500/μL	> 1500/μL or > 50% improvement over baseline	--

Group A criteria define the tumor load, group B criteria define the function of the hematopoietic system (or marrow).

*CR (complete remission): all of the criteria have to be met, and patients have to lack disease-related constitutional symptoms; PR (partial remission): at least two of the criteria of group A plus one of the criteria of group B have to be met; SD is absence of progressive disease (PD) and failure to achieve at least a PR;

PD: at least one of the above criteria of group A or group B has to be met.

†Sum of the products of multiple lymph nodes (as evaluated by CT scans in clinical trials, or by physical examination in general practice).

‡These parameters are irrelevant for some response categories.

From: Hallek et al. Blood. 2008;111(12):5446-56.

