4.8 Efficacy Analysis

4.8.1 Secondary Endpoint

Single efficacy variable analyzed in this study is: **Best Objective Response Rate (ORR)**

(Best) ORR is defined for Cohort A as percentage of patients achieving a complete response (CR), a partial response (PR) or a partial response with lymphocytosis (PRL) at any time during the study, and for Cohort B as percentage of patients achieving a CR or a PR at any time during the study based on the local assessment. CR, PR or a PRL is defined according to the criteria of the International Workshop on Chronic Lymphocytic Leukemia (IWCLL) for CLL patients (Hallek et al., 2008; see Section 6.3), with the modification that treatment-related lymphocytosis in the absence of other signs or symptoms of disease progression will not be considered as progressive disease (Cheson et al., 2012; Hallek et al., 2012; NCCN NHL 2015 Guidelines). For patients with SLL, assessments will be performed using the Lugano Classification criteria for SLL patients (Cheson et al., 2014). The number of patients and rates will be reported split by cohort.

For derivation of the best ORR, response assessments after a patient has started a new anti-neoplastic therapy will not be taken into account.

Response evaluations (CR, PR, PRL, SD and PD) will be tabulated with counts and percentages for each available visit. Missing response evaluations, or non-evaluable assessments will be taken into account, with patients with missing responses included in the denominator for calculating rates.

The above summary/analysis will be performed using the FAS and PPS.

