6.3 Appendix C: Response Definition for CLL by the IWCLL Guidelines 2008

Parameter	CR*	PR*	PD*
Group A			
Lymphadenopathy†	None > 1.5 cm	Decrease \geq 50%	Increase \geq 50%
Hepatomegaly	None	Decrease \geq 50%	Increase \geq 50%
Splenomegaly	None	Decrease \geq 50%	Increase \geq 50%
Blood lymphocytes	< 4000/ μ L	Decrease \geq 50% from baseline	Increase \geq 50% over baseline
Marrow‡	Normocellular, < 30% lymphocytes, no B-lymphoid nodules Hypocellular marrow defines CRi	50% reduction in marrow infiltrate, or B-lymphoid nodules	--
Group B			
Platelet count	> 100,000/ μ L	> 100,000/ μ L or increase \geq 50% over baseline	Decrease of \geq 50% from baseline secondary to CLL
Hemoglobin	> 11 g/dL	> 11 g/dL or increase \geq 50% over baseline	Decrease of > 2 g/dL from baseline secondary to CLL
Neutrophils‡	> 1500/ μ L	> 1500/ μ L or > 50% improvement over baseline	

Group A criteria define the tumor load, group B criteria define the function of the hematopoietic system (or marrow).

*CR (complete remission): all of the criteria have to be met, and patients have to lack disease-related constitutional symptoms; PR (partial remission): at least two of the criteria of group A plus one of the criteria of group B have to be met; SD is absence of progressive disease (PD) and failure to achieve at least a PR; PD: at least one of the above criteria of group A or group B has to be met.

CRi: complete response with incomplete marrow recovery

†Sum of the products of multiple lymph nodes (as evaluated by CT scans in clinical trials, or by physical examination in general practice).

‡These parameters are irrelevant for some response categories.

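### An isolated lymphocyte rise in Cohort B CLL is PD, not PD, or PD unless treatment-related, depending on the section used, and the same gap reaches PR and so ORR

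*Protocol*

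**What the plan says.** These places decide how a lymphocyte rise counts in CLL.

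- **Protocol 9.3.3.2, definitive PD list.** It covers new disease, worsening of nodes, spleen, liver or non-index disease, transformation, and a fall in platelets or hemoglobin due to CLL. It has no lymphocyte item for either cohort.
- **Protocol 9.3.3.2, Lymphocytosis During Therapy.** The reason given is "Upon initiation of idelalisib treatment, transient increase of absolute lymphocyte count is expected in most patients because idelalisib can mobilize CLL cells from tissues". The operative sentence is general: "Subjects with lymphocytosis without any of these other events will not be considered to have progressed and should be continued on study drug". The paragraph also says that lymphocytosis by itself does not block PR when the remaining PR criteria are met. Its only cohort limit is "Note: PRL is applicable in Cohort A only".
- **Protocol 9.3.3.2, PR list.** Every item must be met, including a fall of at least 50% in blood lymphocytes.
- **Protocol 9.3.3.1 and 12.6.1, SAP 4.8.1.** IWCLL 2008 applies, in the SAP's words, "with the modification that treatment-related lymphocytosis in the absence of other signs or symptoms of disease progression will not be considered as progressive disease". Section 9.3.3.1 inserts the same note about PRL. The other two carry no cohort limit on this modification.
- **Protocol Appendix J and SAP 6.3.** The PD entry for blood lymphocytes is "Increase ≥ 50% over baseline", and one criterion is enough: "PD: at least one of the above criteria of group A or group B has to be met".
- **Protocol 6.2.2.** ORR is CR, PR or PRL in Cohort A, but only CR or PR in Cohort B.
- **Protocol 7.1.** PD requires study medication to stop. Also: "In case idealisib or venetoclax treatment was stopped due to side effects suspected to be related to idealisib or venetoclax, the patient may continue MOR00208".

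**The concern.** The rationale for the exemption covers one drug, while the operative text covers all subjects. The appendix tables then list the exempted finding as PD once it reaches 50% over baseline. Response is called locally, so two sites can record the same blood picture differently without either departing from the protocol.

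Those calls fill the by-visit response tables, decide when treatment stops, and so affect time on study. Through the PR wording they can also decide whether a Cohort B patient counts as a responder.

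**Working it through.** The plan states no figure to reproduce: Protocol 12.1 reports no formal sample size calculation. The check sets the passages side by side on constructed cases.

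**Case 1: PD in Cohort B.** A CLL patient has a lymphocyte count of 100 at baseline and 160 ×10⁹/L now. The change is (160 − 100)/100 = +60%. Nothing else has worsened.

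- 9.3.3.2, PD list: no item is met, so not PD.
- 9.3.3.2, lymphocytosis paragraph: not PD, and study drug continues.
- Appendix J and SAP 6.3: 60% exceeds 50% and one criterion suffices, so PD. Section 7.1 then requires study medication to stop.
- 9.3.3.1, 12.6.1 and SAP 4.8.1: not PD only if the rise is judged treatment-related. No rule for that judgement is given, and the only mechanism described is idelalisib's.
- 9.3.3.1, imaging text: suspected progression should be confirmed by CT. A scan with stable nodes cannot confirm progression seen only in blood.

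**Case 2: Cohort A after idelalisib.** MOR00208 may continue alone after idelalisib toxicity (7.1) or after a confirmed response with marrow MRD negativity (9.2.7). The lymphocytosis paragraph says the idelalisib effect can persist, but sets no end to the exemption once the drug is stopped. The readings in Case 1 then apply again.

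**Case 3: PR in Cohort B.** The count is again up 60%, but nodes and spleen have shrunk by at least half and the blood-count condition for PR is met.

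- 9.3.3.2, PR list: the 50% lymphocyte fall is missing, so not PR. With no PD item met either, the call is SD.
- 9.3.3.2, lymphocytosis paragraph: PR is not blocked.
- Appendix J and SAP 6.3: a PD criterion is met.

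In Cohort A the PRL category takes up this picture and counts in ORR. In Cohort B it is not available.

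**Precedence.** Section 9.3.3.2 points to Appendix J without ranking it. Protocol 12 says the SAP prevails where the two differ. But SAP 4.8.1 both states the modification and refers to SAP 6.3, which holds the contrary criterion.

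**Size.** One patient in a cohort of 12 is 1/12 = 8.3 points. At 10 patients, the lower end of the planned range, it is 1/10 = 10 points. This applies directly to a by-visit rate. ORR moves by that amount only in two situations:

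- the PR wording changes whether a patient is a responder (Case 3);
- a PD call on lymphocytes alone comes before the first response and ends treatment or, under 9.3.3.2, the period over which best response is taken.

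**The case against.** The strongest reply is that the order of authority is mostly clear. Section 9.3.3.1 applies IWCLL 2008 as modified, and Appendix J is simply the unmodified source table. The lymphocytosis paragraph opens with idelalisib and, read in context, concerns idelalisib. For Cohort A patients taking idelalisib this stands: the conflict is largely settled there. It does not settle Cohort B. The modification depends on a term that is undefined for venetoclax or for MOR00208 alone, the operative sentence names no cohort, and the PD list omits lymphocytes for everyone.

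A second reply is that the CT rule stops sites from ending treatment on a blood count. That weakens the claim about treatment stopping. It also leaves the appendix's lymphocyte criterion unusable by itself, which is a further mismatch.

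Some stronger readings are tempting but not supported:

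- *The protocol expressly exempts Cohort B.* It does not. The wide scope follows from the absence of a limit.
- *Appendix J calls any lymphocytosis PD.* It requires a rise of at least 50% over baseline.
- *A late relapse in blood inflates Cohort B ORR.* SAP 4.8.1 counts a response achieved at any time in the study, so later PD does not remove it.
- *Measuring lymphocytes from baseline is an error because nodes are measured from nadir.* A count going from 100 to 2 to 120 is 20% over baseline and is PD under neither 9.3.3.2 nor Appendix J. The documents do not contradict each other there, and the choice of reference is largely a preference.

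**Conclusion.** The contradiction holds for Cohort B CLL patients, and for Cohort A patients who have stopped idelalisib and continue MOR00208, when lymphocytes rise at least 50% over baseline with no other sign of progression. The documents give three answers: not PD, PD, and not PD only if treatment-related. The PR wording has a related gap, so Cohort B ORR can depend on which passage a site follows.

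The size is 8.3 points per reclassified patient in a by-visit rate, assuming 12 patients in the denominator. For ORR it applies only through the PR wording or an early PD call. The documents give no basis for estimating how often such patients occur. The primary endpoint, adverse events, is touched only indirectly through time on treatment. SLL patients are assessed by the Lugano criteria and are outside this point.

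**What to change.** Reconcile Protocol 9.3.3.1, 9.3.3.2, 12.6.1 and Appendix J with SAP 4.8.1 and 6.3:

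- Give one lymphocyte rule for PD and one for PR, each with its cohort and treatment-period scope and a single stated reference value.
- Define treatment-related, or drop the term.
- State which prevails, 9.3.3.2 or the appendix tables, and annotate the tables to match.
- Align the rule with the CT-confirmation text in 9.3.3.1.
- Apply the agreed rule consistently in the by-visit response tables and ORR, using the lymphocyte counts already collected.

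Because PD governs stopping of treatment, the choice of clinical rule belongs to the sponsor and none is proposed here. The cost is wording in both documents, with no new data collection. Some Cohort B calls may become slightly less favourable.

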9.3.3.3 Tumor Response Assessment for SLL

Tumor measurements will be performed by CT as indicated in [Table 12](#). MRI may be used in lieu of CT for patients with contraindications to the administration of contrast agents, or due to other medical reasons, at the same timepoints as CT or, in addition to CT, at the discretion of the Investigator (in this case, MRI may be performed as/when appropriate).

Table 12: Lugano Classification Criteria for SLL (adapted from Cheson et al., 2014)

Response	Site	CT-Based Response
CR	Lymph nodes and extralymphatic sites Nonmeasured lesions Organ enlargement New lesions Bone marrow	Complete remission requires all of the following: Target nodes/nodal masses must regress to ≤ 1.5 cm in LDi No extralymphatic sites of disease Absent Regress to normal None Normal by morphology; if indeterminate, IHC negative
PR	Lymph nodes and extralymphatic sites Nonmeasured lesions Organ enlargement New lesions Bone marrow	Partial remission requires all of the following: $\geq 50\%$ decrease in SPD of up to 6 target nodes and extranodal sites When a lesion is too small to measure on CT, assign 5 mm x 5 mm as the default value When no longer visible, 0 x 0 mm For a node > 5 mm x 5 mm, but smaller than normal, use actual measurement for calculation Absent/normal, regressed, but no increase Spleen must have regressed by $> 50\%$ in length beyond normal (13 cm) None Normal marrow, persistent infiltration, or no marrow obtained
SD	Target nodes/nodal masses/extranodal lesions Nonmeasured lesions Organ enlargement New lesions Bone marrow	Stable disease $< 50\%$ decrease from baseline in SPD of up to 6 target nodes and extranodal sites; no criteria for progressive disease are met No increase consistent with progression No increase consistent with progression None Normal marrow, persistent infiltration, or no marrow obtained
PD	Individual target nodes/nodal masses	Progressive disease requires at least 1 of the following: PPD progression

Response	Site	CT-Based Response
PD	Extranodal lesions	An individual node/lesion must be abnormal with: LDi > 1.5 cm and Increase by $\geq 50\%$ from PPD nadir and An increase in LDi or SDi from nadir 0.5 cm for lesions ≤ 2 cm 1.0 cm for lesions > 2 cm In the setting of splenomegaly, the splenic length must increase by > 50% of the extent of its prior increase beyond baseline (e.g., a 15-cm spleen must increase to > 16 cm). If no prior splenomegaly, must increase by at least 2 cm from baseline New or recurrent splenomegaly
	Nonmeasured lesions	New or clear progression of preexisting nonmeasured lesions
	New lesions	Regrowth of previously resolved lesions A new node > 1.5 cm in any axis A new extranodal site > 1.0 cm in any axis; if < 1.0 cm in any axis, its presence must be unequivocal and must be attributable to lymphoma Assessable disease of any size unequivocally attributable to lymphoma
	Bone marrow	New or recurrent involvement

Abbreviations: CR=complete remission; PR=partial remission; SD=stable disease; PD=progressive disease; CT=computed tomography; LDi=longest transverse diameter of a lesion; IHC=immunohistochemistry; SPD=sum of the product of the perpendicular diameters for multiple lesions; PPD=cross product of the LDi and perpendicular diameter; SDi=shortest axis perpendicular to the LDi.

9.3.3.4 Bone Marrow Aspiration and Biopsy

For patients with CR, a bone marrow aspiration and biopsy has to be performed for confirmation of CR at least 8 weeks after the CR criteria for tumor response were first met. The results of the CT scan need to be obtained first; if this does not confirm a CR, then a BM aspiration/biopsy should not be performed. Histological examination of the bone marrow should be performed locally. Furthermore, patients who achieved a PR and PB MRD negativity need also to perform a bone marrow aspiration/biopsy.

9.3.3.5 B-Symptoms

B-symptoms are defined as any one or more of the disease-related symptoms or signs mentioned in [Appendix K](#). Assessment of the presence or absence of B-symptoms will be performed at screening and on Day 1 of all cycles, as well as the EOT visit, and at the 30-Day Safety Follow-up visit. B-Symptoms will also be assessed in case a patient will be followed up for disease progression after the EOT visit, as described in the Schedule of Assessments ([Table 10](#)). B-symptoms should not be reported as AEs. Worsening is generally considered a symptom (but not an objective criterion) of progression.

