A pivotal phase III study investigated idelalisib at a dose of 150 mg twice daily in combination with RTX versus RTX single agent treatment in R/R CLL patients deemed ineligible for further cytotoxic chemotherapy because of significant myelosuppression related to previous chemotherapy, creatinine clearance (CrCl) < 60 mL/min, or a Cumulative Illness Rating Scale (CIRS) value > 6 (Furman et al., 2014).

Compared with single agent RTX, combination therapy resulted in a significantly higher rate of PFS at 24 weeks (93% vs. 46%) and a significantly higher 12-month overall survival rate

(92% vs. 80%). The ORR among patients receiving combination therapy was impressive (81% vs. 13% for RTX only); see [Table 1](#).

Table 1: Efficacy of Idelalisib in Relapsed CLL in Phase III Trial of Idelalisib plus Rituximab Versus Placebo plus Rituximab (Furman et al., 2014)

	Idelalisib plus Rituximab (N=110)	Placebo plus Rituximab (N=110)	
Median PFS (primary endpoint)	Not reached ¹	5.5 months	
Rate of PFS at 24 weeks	93%	46%	HR = 0.15, P < 0.001
Rate of OS at 12 months	92%	80%	HR = 0.28, P = 0.02
Overall response rate	81%	13%	OR = 29.92, P < 0.001

¹ Disease progression occurred in only 12 patients.

Abbreviations: PFS=progression-free survival; OS=overall survival; HR=hazard ratio; OR=odds ratio.

The most common adverse events (AEs) in the idelalisib/RTX group ($\geq 15\%$) were: pyrexia, fatigue, nausea, chills, diarrhea, infusion-related reaction (IRR), and cough. The majority of the AEs were Grade 1 or 2. Most common ($\geq 5\%$) serious adverse events (SAEs) were pneumonia, pyrexia, and febrile neutropenia. The AE profile observed for the combination therapy was not significantly different from that observed for the single agent idelalisib studies in particular the study described above on 125 patients with indolent B-NHL entities (Gopal et al., 2014).

The European Medicines Agency's Pharmacovigilance Risk Assessment Committee has most recently carried out a safety review started after a higher rate of serious adverse events related to infections, such as pneumonia, occurred. These were seen in three clinical trials among patients, who received idelalisib in addition to other cancer medicines. In its conclusion, Committee for Medicinal Products for Human Use had confirmed, that the medicine's benefits outweigh its risks in the treatment of CLL.

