Please note that in the context of this protocol symptoms that are clearly associated to the progression of underlying malignancy (CLL/SLL) do not fall under the definition of AEs.

Each AE should be evaluated to determine the following:

- Relationship to the study drug (suspected/not suspected)
- Duration (start and end date, or if continuing at end of study)
- Intensity: the intensity of all AEs will be graded as mild, moderate, or severe using the following definitions:
 - mild: tolerable
 - moderate: interferes with normal activity
 - severe: incapacitating (causes inability to perform usual activities or work)
- Severity, i.e., toxicity grade: determined according to the NCI-CTCAE version 4.03 of June 14, 2010 (or higher), using the following definitions:
 - grade 1: mild; asymptomatic or mild symptoms; clinical or diagnostic observations only; intervention not indicated
 - grade 2: moderate; minimal, local or noninvasive intervention indicated; limiting age-appropriate instrumental activities of daily living (refers to preparing meals, shopping for groceries or clothes, using the telephone, managing money, etc.)
 - grade 3: severe or medically significant but not immediately life-threatening; hospitalization or prolongation of hospitalization indicated; disabling; limiting self-care activities of daily living
 - grade 4: life-threatening consequences; urgent intervention indicated
 - grade 5: death related to AE
- Outcome
- Action taken (no action taken; study drug temporarily interrupted; study drug permanently discontinued due to this AE; medication taken; non-drug therapy given; hospitalization/prolonged hospitalization)
- Seriousness: whether it is serious, **where an SAE is defined as one that:**
 - results in death
 - is life-threatening
 - requires inpatient hospitalization or prolongation of existing hospitalization (hospitalization signifies that the patient was an inpatient for at least one overnight stay) **unless hospitalization is for:**
 - routine treatment or monitoring of the studied indication, not associated with deterioration of symptoms related to CLL/SLL

- elective or preplanned treatment for a pre-existing condition that is unrelated to CLL/SLL and has not worsened since signing of the informed consent
- social reason and respite care in the absence of any deterioration in the patient's general condition
- results in persistent or significant disability or incapacity
- is a congenital anomaly or birth defect

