15.11 Appendix K: Criteria for B-Symptoms

Criteria for B-Symptoms

The presence of:

- a) unintentional weight loss of more than 10% within the previous 6 months and/or
- b) fevers of greater than 100.5°F or 38.0°C for at least 3 consecutive days without other evidence of infection and/or
- c) drenching night sweats without evidence of infection

is denoted by the suffix letter 'B'.

'A' indicates the absence of these symptoms.

MorphoSys AG Proprietary Information

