4.10.7 B-Symptoms

B-symptoms are defined as any one or more of the following disease-related symptoms or signs:

- Unintentional weight loss of $\geq 10\%$ within the preceding 6 months or less.
- Drenching night sweats without signs of infection.
- Recurrent, unexplained fever with temperatures above 38°C without signs of infection.

The presence of B-symptoms will be summarized categorically in a frequency table by visit. The analysis will be performed on the SAF. Data listings will be presented.

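### Protocol 9.3.3.5 keeps all B-symptoms out of AE reporting, which conflicts with the progression-only exemption in Protocol 10.1 and SAP 4.10.1 and can remove new or worsened symptoms from the primary endpoint

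*Protocol*

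**What the plan says.** Protocol 9.3.3.5 opens with a definition: "B-symptoms are defined as any one or more of the disease-related symptoms or signs mentioned in" Appendix K. It schedules a present-or-absent assessment at screening, on Day 1 of every cycle, at end of treatment and at the 30-day follow-up. It then says "B-symptoms should not be reported as AEs. Worsening is generally considered a symptom (but not an objective criterion) of progression".

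Appendix K lists three criteria. The fever criterion is "fevers of greater than 100.5°F or 38.0°C for at least 3 consecutive days without other evidence of infection". Night sweats carry the same infection exclusion. Unintentional weight loss above 10% in six months carries no exclusion of any cause.

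Protocol 10.1 defines an AE as any unfavourable sign or symptom, drug-related or not, and includes an increase in a pre-existing condition. Its disease exemption is narrow: "symptoms that are clearly associated to the progression of underlying malignancy (CLL/SLL) do not fall under the definition of AEs". SAP 4.10.1 repeats both the definition and the exemption. AE incidence and severity is the primary endpoint (Protocol 6.2.1).

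SAP 4.10.7 tabulates B-symptoms by visit on the safety set. It words the fever criterion as "Recurrent, unexplained fever with temperatures above" 38°C, with no minimum duration, and sets weight loss at 10% or more. SAP Appendix D keeps the Appendix K wording.

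**The concern.** The two sections give a site different instructions for the same event. Section 9.3.3.5 removes every B-symptom from AE reporting, whether it was there at screening or began on treatment, and whether or not the disease has progressed. Section 10.1 removes only symptoms clearly tied to progression.

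The overlap with known drug effects makes this more than editorial. Protocol 4.3 gives the common AEs of idelalisib plus rituximab (15% or more) as "pyrexia, fatigue, nausea, chills, diarrhea, infusion-related reaction (IRR), and cough". Protocol 5.6 includes pyrexia among venetoclax reactions above 15%, and Protocol 4.5.3 lists it as an anticipated MOR00208 risk. A fever above 38.0°C lasting three days with no infection found meets Appendix K whether the cause is the leukemia or a study drug.

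An event filed only as a B-symptom gets no CTCAE grade, causality or action taken under the sections that describe it. B-symptoms are also not named among the items for the IDMC's run-in review in Protocol 10.4, although that list allows other relevant safety data as necessary. Any error runs toward fewer AEs.

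**Working it through.** The plan gives no figure to reproduce: the analysis is descriptive and has no sample size calculation (Protocol 12.1). The check is a comparison of the two rules, followed by simple arithmetic for scale.

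**Step 1. Apply both rules to the same on-treatment event.**

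| Event after first dose | Protocol 9.3.3.5 | Protocol 10.1 and SAP 4.10.1 |
|---|---|---|
| Present at screening, unchanged | Not an AE | Not an AE (no increase) |
| Clearly tied to progression | Not an AE | Not an AE |
| New or worsened, attributed to CLL, no progression | Not an AE | AE |
| New or worsened, cause uncertain, meets Appendix K | Can be filed as a B-symptom, so not an AE | AE |
| Judged drug-caused or infectious | Not disease-related, so outside the section | AE |

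The rules disagree in rows three and four only.

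**Step 2. Does 9.3.3.5 make every worsening progression?** If it did, 10.1 would exempt row three as well. But 9.3.3.5 itself says worsening is not an objective criterion. Protocol 9.3.3.2 goes further: constitutional symptoms that worsen without objective worsening of CLL are not definitive progression, and causes other than CLL should be considered. Such a symptom is hard to call clearly associated with progression, so the conflict stands.

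**Step 3. Weight of one patient.** With N = 12 per cohort (Protocol 12.1; approximately 12 in SAP 3.10), 1/12 = 8.3 percentage points. Exact (Clopper-Pearson) 95% intervals:

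- 0/12 = 0% (0 to 26.5%)
- 1/12 = 8.3% (0.2 to 38.5%)
- 2/12 = 16.7% (2.1 to 48.4%)

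Moving one patient takes a term from 16.7% to 8.3%, below the 10% cut for most common AEs in SAP 4.10.1.6.1.

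**Step 4. How many patients might have a fever at all.** Expected number = 12 × rate.

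- MOR00208 phase I, all doses (Protocol Table 2): 4/27 = 14.8%; 12 × 4/27 = 1.8 patients; P(at least one) = 1 − (23/27)^12 = 0.85.
- Same table, 12 mg/kg only, this trial's dose: 1/16 = 6.3%; 12 × 1/16 = 0.75 patients; P(at least one) = 1 − (15/16)^12 = 0.54.
- MOR00208 in Protocol 5.6: at most 8%; 12 × 0.08 = 0.96 patients at most.
- Partner drugs at 15%: 12 × 0.15 = 1.8 patients.

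At each assumed rate these count patients with any fever. They are a ceiling on fevers open to misfiling, because only those meeting the duration and no-infection criterion could qualify. The documents give neither that share nor rates for weight loss or night sweats.

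**The case against.** The strongest reply is that disease-related in the opening sentence of 9.3.3.5 is the attribution test and Appendix K only supplies thresholds. On that reading a drug fever is never a B-symptom and 10.1 captures it. Several other rules also catch fever. Neutropenia with fever or infection at grade 3 or above is an AE of special interest for venetoclax (10.1). Table 8 places neutropenic fever under hematological adverse events for Cohort A. Fever during an infusion reaction is reported with that reaction (10.5). Clinically significant vital signs at infusion monitoring, temperature included, must be recorded as an AE (9.3.2.2). B-symptoms are tabulated and listed, and temperature is summarized with abnormal values flagged, so nothing disappears from the safety data.

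Most of this stands, and it rules out three stronger readings.

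- A reader might infer that 9.3.3.5 removes all new fever, weight loss or sweats whatever the cause. The opening sentence and the infection exclusions contradict that.
- A reader might multiply a pyrexia rate by an assumed share of qualifying fevers to get a number of AEs lost. No such share is in the documents, and the MOR00208 rate depends on whether doses are pooled.
- A reader might infer that the SAP 4.10.7 definition diverts further events from AE reporting. It governs a table, not what sites enter, and by requiring recurrence it is not simply looser.

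The reply does not remove the conflict. No section says who decides that a symptom is disease-related, or how. Even with perfect attribution, row three of the comparison is still an AE under 10.1 and barred under 9.3.3.5.

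**Conclusion.** The rule in 9.3.3.5 is wrong as written: it is broader than the exemption in 10.1 and SAP 4.10.1, and a site cannot follow both. The events at risk are new or worsened B-symptoms that are of uncertain cause, or attributed to CLL/SLL without progression. Each patient affected is 8.3 points of a 12-patient cohort, in the direction of fewer AEs. How many patients that would be cannot be derived from the documents. It is probably small, given the other reporting routes for drug-caused, infectious, neutropenic and infusion-related fever.

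Severity is moderate. The conflict touches what enters the primary endpoint, but the analysis is descriptive, the symptoms stay in the by-visit output, and a correction is easy. The conclusion assumes that at least some sites would take 9.3.3.5 literally; it assumes no particular fever rate. The mismatch between SAP 4.10.7 and the two appendices is a separate, smaller inconsistency that blurs the same boundary.

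**What to change.** 1. Replace the sentence in Protocol 9.3.3.5 with, for example: *B-symptoms present at screening and unchanged are not AEs. New or worsened fever, weight loss or night sweats after first dosing are reported as AEs with grade and causality, unless clearly associated with progression (Section 10.1).* This keeps the sensible purpose of the carve-out, which is not to log stable baseline disease symptoms as AEs.
2. Before database lock, query every B-symptom first recorded after C1D1 that has no matching AE. A present-or-absent record cannot show worsening of a symptom already there at baseline, so remind sites separately to report worsening.
3. Align SAP 4.10.7 with Protocol Appendix K and SAP Appendix D: weight loss above 10%, and fever on at least three consecutive days.

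The cost is one protocol sentence, a note to sites, one SAP edit and a few data queries. AE counts may rise slightly. The change concerns reporting only and does not alter treatment.
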